7. STATISTICAL CONSIDERATIONS

The **Primary Outcome Measure** is the proportion of participants in each arm who receive any health service (i.e., STI/pregnancy/HIV testing, condoms, emergency or other hormonal contraception, Adolescent Clinic referral/visit completion). Visit completion will be measured at 3 weeks; all others at initial ED visit.

Feasibility Measures: All participants: (1) proportion of eligible patients enrolled; (2) proportion rating screening survey as very/fairly satisfactory; and (3) proportion completing follow-up. Intervention arm: (1) proportion completing intervention; (2) proportion in which 75% of recommendations are discussed; (3) proportion rating intervention as very/fairly satisfactory; and (4) counseling session time. We will examine length of stay for participants vs. non-participants and costs.

We use items adapted from national surveys to assess risk behaviors. We will use an audio computer-assisted self-interview (ACASI) to reduce social desirability bias and literacy barriers. Follow-up will be completed via web-based surveys or telephone.

Sample size: In a review of 130 patients, we found the pre-intervention proportion of ≥ 1 service uptake was .08. Our pilot study provided an estimate of the post intervention proportion of .65. We used conservative estimates for differences in uptake rates between arms, inflating the control to .15 (vs. .08), deflating the intervention to .50 (vs. .65). With these estimates, an alpha of .05 and a sample size of 76 participants (38 each arm) we achieve a power of .94, well above the usual .80. Given that our primary outcome will be measured at 3 weeks, and our historical attrition rate has been low, we will recruit only four additional participants (N=80) to protect against attrition. Even with 25% attrition, we would still achieve .84/.91 power for two-tail and

one-tail tests respectively. To protect against self-selection or attrition biases, we will randomize arm assignments and analyze potential impacts of attrition.

Hypothesis: The enhanced ED SexHealth intervention will result in statistically significantly higher health service uptake rates versus a standard information arm.

We will compare rates of participants in each arm who complete ≥ 1 health service using tests of the differences between two sample proportions. We expect an effect size of .57 (i.e., .65-.08) which is much higher than used in the sample size estimate (.50-.15=.35). Because we will have power to detect differences as small as .21, we should have more than a sufficient sample size.

Descriptive statistics of the percentages, mean, median, range, as well as confidence intervals, will be used to describe feasibility and theory of planned behavior measures (e.g., attitudes, risk perception), behaviors, and demographics. Appropriate analyses will be performed to examine distributional characteristics of outcome measures and to model temporal changes as a function of group assignments. We will compare rates of condom use using bivariate and multivariate methods that capture arm differences and mediation and moderation covariate influences over time. Demographic characteristics and baseline assessment scores of the two arms will be compared using appropriate chi-square and t tests. Analyses will be done with SPSS Version 21 or SAS 9.3.

Retention Strategies: All youth provide contact methods to receive brief text/email messages, modeled on best practices to facilitate referral completion and study retention. To aid recall, we conduct surveys every 2 months. Compensation will be up to \$85: \$5 for completing the screening survey, \$25 for ED treatment; \$10-25/each telephone or on-line survey completed.

Expected results/outcomes

Upon successful project completion, we will determine if our enhanced ED SexHealth intervention results in increased service uptake rates compared to control and intervention feasibility. Results will provide necessary evidence (e.g., effect size estimates) to support a successful R01 application that proposes a multi-site clinical trial to evaluate efficacy. This trial may provide further justification that improved access to effective services is cost-effective and reduces the financial and social burden of HIV, STIs, and unintended pregnancy in the U.S.

Limitations, barriers, and responsive solutions

We considered these potential limitations. 1) This plan may be difficult to execute. However, our experiences and the literature demonstrate that ED-based interventions can work. 2) To protect against difficulty achieving sample size or higher than anticipated dropout rates, we planned incentives and used a conservative estimate for follow-up. 3) We use ACASI to reduce social desirability bias and literacy barriers. 4) Contamination threat is minimal as the intervention is conducted by personnel not available for control or non-study participants.

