1. STUDY OBJECTIVES/HYPOTHESIS

Primary Objective(s)

To enhance and test our ED SexHealth intervention that provides risk reduction counseling and point-of-care services as well as connections to sustainable, non-episodic sources of care.

Hypothesis 1: The enhanced ED SexHealth intervention will result in statistically significantly higher health service uptake rates versus a standard information arm.

Hypothesis 2: The enhanced ED SexHealth intervention will be feasible, as measured by qualitative and quantitative data from adolescents, health educators, ED providers and hospital administrators.

2. BACKGROUND and RATIONALE

Although highly preventable, STIs/HIV and unintended pregnancy are significant and costly public health problems that disproportionately impact adolescents, especially minority and uninsured youth.¹⁻³ While these disparities result from a complex convergence of patient, provider, and health systems factors, limited access to care directly contributes to these disparities, independent of race/ethnicity.⁴⁻⁸ Adolescents make 19 million Emergency Department (ED) visits each year and frequently report intercourse not protected against STI/HIV or pregnancy.⁹⁻¹⁰ Further, among these youths, rates of infection with chlamydia and gonorrhea are up to 7 times higher than the general population.¹¹⁻¹⁴

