We will collect immediate post-intervention survey data from all participants. The health educator will complete a survey following each intervention. We will collect data on health services (i.e., STI/pregnancy testing, condoms, emergency contraception, hormonal contraception, STI treatment, HIV testing, referral to clinic) offered, accepted, and completed as well as services provided as part of ED clinical care. When determining completion of sexual health services, services that are completed via a standing order or protocol (e.g., adolescent female receiving urine pregnancy test before radiographic imaging) will be noted and not included when determining our outcome measurement.

Incentives

Compensation for the formative group will be up to \$55.00.

Part 1 Take survey	Part 2 Meet with the Health Educator	Part 3 Take survey about meeting with the Health Educator
\$5.00	\$30.00	\$20.00

Compensation for the RCT will be up to \$80:

\$5 for completing the screening survey, if the subject does not qualify or decides not to continue in the study, their participation will be over and they will receive a \$5.00 Target® gift card.

If a subject qualifies to continue in the study and signs the written consent they will receive a Greenphire Clincard instead of the Target® card. If they continue in the study they will be randomized into study group. At the end of this visit they will receive the Greenphire Clincard gift card. It will be uploaded with \$5.00 for taking the computerized survey and \$30 for completing the randomization part of the visit for a total of \$35.00. An additional \$10-each will be loaded onto the Greenphire Clincard when month 2 and month 4 surveys are completed and final \$25 for month 6 survey completion. All surveys can be completed online or by telephone. All health services (e.g., STI testing, condoms) will be provided at no cost to participants in the intervention arm. Charges for any service for participants in the control arm will be billed by the ED provider according to their standard practice.

Visit 1 (screening)	Visit 1 (randomization)	2 mo.	4 mo.	6 mo.
Take computerized screening survey \$5.00	Be randomized into study group and complete assigned arm procedures \$30.00	Take survey online or by phone \$10.00	Take survey online or by phone \$10.00	Take survey online or by phone \$25.00

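### Does the loose wording of the clinic component leave the primary outcome open to two scorings that matter?

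*Combined protocol and SAP*

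**What the plan says.** Section 7, Primary Outcome Measure, defines the outcome as the proportion in each arm who *receive* any service. The list closes with "emergency or other hormonal contraception, Adolescent Clinic referral/visit completion). Visit completion will be measured at 3 weeks; all others at initial ED visit". The analysis paragraph of the same section uses a different verb: "We will compare rates of participants in each arm who complete" at least one service. The sample size paragraph treats the outcome as known only at the later time point: "Given that our primary outcome will be measured at 3 weeks".

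Section 3 (Study Design), Data Collection, records services in separate states: "STI treatment, HIV testing, referral to clinic) offered, accepted, and completed as well as services provided as part of ED clinical care". It has one scoring rule, which begins "When determining completion of sexual health services, services that are completed via a standing order or protocol" and removes such services from the outcome. It does not mention unattended appointments.

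The arms differ on this item. Under Section 3, the intervention arm may be offered a scheduled Adolescent Clinic appointment. Controls get a pamphlet and a resource list with the clinic's phone number, then their ED provider's usual care.

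**The concern.** The slash between referral and visit completion can be read in two ways. If it separates two items, a referral accepted in the ED is already a success. Section 1 gives that reading some footing, because the primary objective covers point-of-care services "as well as connections to sustainable, non-episodic sources of care". If the slash means completion of the referral, only an attended visit counts. A participant whose sole service is an accepted but missed appointment is a success on the first reading and a failure on the second.

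Such participants would sit mainly in the intervention arm, since only that arm is offered an appointment booked by the study. Two analysts could therefore report different intervention rates from the same data while the control rate hardly moved. The estimate has a planned use: "Results will provide necessary evidence (e.g., effect size estimates) to support a successful R01 application". If the rule were picked after seeing results by arm, the choice could favour the intervention. A smaller mismatch is that Section 3 lists STI treatment as a service and the Section 7 list omits it.

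**Working it through.** **1. Where the wording can change a score.** Tests, condoms and contraception are provided in the ED. Someone who receives one of these has, for nearly all purposes, completed it. The choice of verb matters only for the clinic item, and only for a participant with no other counted service.

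**2. Which way the text leans.**

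| Place | Points to |
|---|---|
| Section 7, analysis sentence: complete | attendance |
| Section 3, scoring rule: completion | attendance |
| Section 7, sample size: outcome known at 3 weeks | attendance |
| Section 7, Retention Strategies: messages "modeled on best practices to facilitate referral completion and study retention" | attendance |
| Section 7, definition: receive, and the slash | either |
| Section 3: referral listed as a service | accepted referral |

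If acceptance were enough, everyone who accepted in the ED would already be a success. The 3-week measure could then add only people who attended without a counted referral, and the attrition argument tied to 3 weeks would have little purpose in the intervention arm. Attendance is the more coherent reading, although it is not stated outright.

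**3. The plan's own power figure.** Inputs from Section 7: .15 versus .50, alpha .05, 38 per arm. With unpooled variance and a two-sided test:

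- SE = √[(.15×.85 + .50×.50)/38] = .0997
- .35/.0997 = 3.51
- power = Φ(3.51 − 1.96) = .94, as stated

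The .84 two-tailed figure after 25% attrition (80 × .75 = 60, so 30 per arm) reproduces as .843 with pooled variance under the null.

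**4. How many referral-only no-shows would overturn the test.** Assumptions: 40 per arm, and controls at 6/40 (the planning rate .15). The test is the pooled two-proportion z, two-tailed: z = (p₁ − p₀)/√[2p̄(1 − p̄)/40], where p̄ is the pooled rate. The number reclassified is assumed, because the documents do not give it.

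| Intervention | Difference (points) | z | p |
|---|---|---|---|
| 20/40 | 35 | 3.34 | .0008 |
| 16/40 | 25 | 2.50 | .012 |
| 14/40 | 20 | 2.07 | .039 |
| 13/40 | 17.5 | 1.84 | .066 |

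Significance is lost at 13/40. The reclassifications needed are:

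- from .50: 20 − 13 = 7 of 20 successes (35%)
- from the version 1 pilot's .65 (26/40): 26 − 13 = 13 of 26 (50%)
- from the version 2 pilot's .75 (30/40): 30 − 13 = 17 of 30 (57%)

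With controls at 3/40, near the observed .08, the limit moves down to 9/40 (z = 1.88, p = .060). It then takes 26 − 9 = 17 of 26 (65%) or 30 − 9 = 21 of 30 (70%).

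**5. Is such a large group plausible?** Section 3 offers the intervention arm several free services on the spot. In version 2 (Section 2, Preliminary work) the system made 3.9 recommendations per participant, and the educator discussed 77% of all recommendations. This does not fix the number, but it suggests that few participants would leave with a clinic appointment and nothing else.

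**6. Can both scorings be recovered?** Yes. Section 3 records accepted and completed services separately, and Appendix 1 schedules a chart review of service use at 3 weeks. No new data are needed.

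**The case for a change.** The strongest case for acting is that a primary outcome should have one scoring rule, fixed before results are seen by arm, and that adding one would cost a sentence. The effect of the gap is one-sided, and the estimate moves with every affected participant even when the p-value stays small. The word referral is not defined either, so verbal advice from a control's ED provider could be scored either way. All of that stands as a reason for care in coding the outcome.

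A further argument is that requiring attendance would lower power. If .50 already counts missed appointments, scoring 5 or 10 points of it as failures takes power at 40 per arm from .93 to .85 or .71. This part does not stand. Section 2 words the version 1 pilot rate of .65, from which .50 was derived, as participants who completed at least one service. It does not say whether attendance was needed, so nothing in the documents supports treating .50 as the lenient rate and subtracting again. The plan had also already cut .65 by 15 points.

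The omission of STI treatment from the Section 7 list is a slip of little consequence. That service is offered only for an infection already diagnosed and untreated, and it matters only if the participant received nothing else.

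**Conclusion.** No change to the plan is called for. The wording leaves a gap that a competent analyst would fill sensibly. The text favours an attended visit by 3 weeks, counting an accepted referral would also be defensible given the objective, and the data allow both rates to be shown by arm. No stated number or rule is wrong, and the plan's power figures reproduce.

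The size is 2.5 points on the difference for each participant whose only service is a missed appointment. With controls at 6/40, the test result changes only if such participants make up 35% of intervention successes at .50, 50% at .65 or 57% at .75. These figures assume 40 analysed per arm, the pooled z test, and reclassification in the intervention arm only. The actual number of such participants is unknown. The conclusion would weaken if most intervention successes turned out to be clinic referrals with no other service, which the range of free services in the ED makes unlikely.

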3. STUDY DESIGN

This is an adaptive trial with an initial **Formative Revision Process** followed by a **Randomized Controlled Trial**. Up to 500 adolescents will be consented into this study to achieve 6 completed subjects for the formative process and 80 completed subjects (40 in each arm) for the RCT. Up to two Health Educators will be consented as secondary subjects who will complete post-intervention assessment survey's.

Formative Revision Process

Based on pilot feedback and relevant literature,¹⁹⁻²³ we made modifications to increase adolescents' motivation for service uptake and safer sex behaviors. To increase motivation, we will: 1) expand opportunities to increase receptiveness to change, 2) emphasize interpersonal skills for educators, 3) increase opportunities to develop discrepancy between behavior and risk, and 4) emphasize need for regular care and how to access it. We will incorporate CDS system-generated recommendations directly into the intervention to facilitate participant risk

comprehension and standardize service provision. We will add behavioral skills training and role play for condom use. The educator will deliver the revised SexHealth intervention with a formative group of 6 adolescents. We will gather feedback on intervention acceptability and feasibility using individual session analysis and in-depth interviews. Sessions will be audio-recorded and coded to provide educator feedback and evaluate fidelity to core MI skills. Each adolescent will also complete an in-depth post-intervention interview, with a separate team member. Interviews will be audio-recorded and written notes taken. Data from session analysis, interviews, and educator feedback will be incorporated into the final version with a targeted length of 30 minutes. Our intervention manual contains highlights of revisions, including tailoring for sexual minorities.

The study will then continue as a two-armed randomized controlled, parallel group design with 80 completed participants.

Randomized Controlled Trial

The **Control Group** will receive a printed health pamphlet and a list of local resources with the phone number for Adolescent Clinic. Participants will then be referred back to their ED provider, who will provide their standard care.

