The **Intervention Group** will receive the same pamphlet as controls and the enhanced ED SexHealth intervention with the educator. Based on behaviors, CDS system recommendations (generated from screening survey responses only for intervention participants), and discussions, participants may be offered testing (for pregnancy, gonorrhea/chlamydia, and/or HIV), hormonal birth control, condoms, emergency contraception (for immediate or future use), treatment for previously diagnosed (yet untreated) infection with gonorrhea/chlamydia, and a scheduled appointment at Adolescent Clinic (for ongoing care, including repeat STI/HIV testing if needed). All services will be provided at point of care, costs will be covered by the study. We will use urine/swab specimens for STI testing (Gen-Probe Inc.) with results available within 7 days. We will contact those with an STI and advise them to seek care at the hospital-affiliated Adolescent Clinic or we can call in a prescription for treatment of Chlamydia. We will use fingerstick blood for HIV testing (Alere North America Inc.) and for those with a reactive screen, we will provide immediate, in-person counseling with a case manager from our community partner (see letter from KC CARE Clinic), obtain a confirmatory test, and arrange for rapid follow-up.

Health Educator

We will recruit a health educator with training in public health and health behavior change. They will receive training including in-depth Motivational Interviewing (MI) training supervised by expert team members. Training will include mock patients for hands-on practice and immediate feedback. Encounters will be audio-taped and coded using the Motivational Interviewing Treatment Integrity Coding system to provide objective feedback. The educator will receive instruction in adolescent sexual health including HIV/STIs, sexual minority issues, contraception, and HIV counseling and testing (in partnership with KC CARE Clinic and the Midwest AIDS Training and Education Center). The educator will discuss the first 6 trial participants with Drs. [name] and [name] and attend a one-day “booster” training halfway through the study (led by Drs. [name] and [name]). All sessions will be audio-recorded; 20% will be randomly selected and evaluated for MI fidelity using accepted techniques.¹⁰²⁻⁰³

Provision of health services

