4. TARGET STUDY POPLUATION SPECIFICS

Recruitment procedures: We will use our electronic tracking system to identify potential participants who will be approached sequentially based on arrival and availability (e.g., we will not interrupt patient care). Patients may be approached in private areas of waiting rooms or treatment spaces. Interested patients will initially complete a screening survey. For subjects reporting no previous sexual activity, their involvement in the study will terminate upon screening survey completion.

For eligible youth who agree to participate during the iterative revision process, all youth will receive the intervention until six adolescents have been enrolled. After that time, all eligible and interested participants will be randomized to treatment or control arm.

Based on prior work demonstrating differences in STI and pregnancy testing due to presence of genito-urinary symptoms, we will ensure balanced allocation of participants reporting genitourinary complaints (i.e., concern for pregnancy/sexually transmitted infection, lower abdominal pain, urinary complaints, genital pain or discharge, or vomiting in a female patient) between treatment groups in a 1:1 ratio. We will generate our randomization sequence using REDCap, which will also host our computerized surveys. We will recruit participants during times when adolescents are more likely to visit the ED, using ED arrival data from the previous year to determine recruitment times and we will weight recruitment shifts based on the proportion of adolescents who presented during each block for weekdays (Monday-Thursday)

and weekends (Friday-Saturday). After survey completion, participants will be randomized to receive the intervention or control arm. Randomization will be assigned based on computer-generated algorithm and using numbered sealed envelopes.

Inclusion/Exclusion Criteria

Inclusion: Part 1 (BASELINE) Adolescents who present for care to the CMH Main ED for any reason who 1) are aged 14-19 years and 2) reside within 30 minutes travel time of CMH will be eligible to complete the computerized health behavior screening survey. We selected thirty minute travel time (per subject self-report) to facilitate potential clinic referral.

Part 2 (INTERVENTION) and (Part 3 Post-Intervention survey for Formative Group)

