8. HUMAN SUBJECTS

Consent of Participants

We will use our electronic tracking system to identify potential participants to complete the computerized health behavior screening survey.

Consent/assent will be completed in two phases: 1) screening for eligibility and GU complaints with the health survey (see "health screening survey") and 2) formative group/randomized trial.

Subjects aged 14-17 years: For phase 1 (screening), potential subjects and parents will be given study information sheet ("info sheet"). Adolescents will independently provide verbal assent, which mirrors the clinical and legal standard for care. For phase 2, study details will be explained in private and written assent obtained from eligible adolescents who agree to

participate. We will request a waiver of parental permission from the institutional review board (IRB) because adolescents 14 years of age or older can seek reproductive care independently in Missouri and Kansas.

Subjects aged 14-17 years seeking ED care for medically emancipated condition: Since many of this subgroup of patients will likely be unaccompanied by a parent, and since they are able to consent for this type of care independently, we will request a waiver of parental permission for both phases from the IRB. For phase 1, potential subjects will be given study information ("info sheet") and will independently provide verbal assent. For phase 2, the study will be explained in private and written assent obtained from those who agree to participate ("minor written assent").

Subjects aged 18-19 years: For both phases, the study will be explained in private ("info sheet"). Subjects will provide verbal consent for phase 1 and written consent for phase 2 ("adult written consent").

Institutional Review Board (IRB) Review and Informed Consent

This protocol, and any subsequent modifications, will be reviewed and approved by the Pediatric IRB at The Children's Mercy Hospital & Clinics.

Subject Confidentiality

The planned procedures for protecting against or minimizing potential risks are described here.

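### The primary test ignores the genitourinary-complaint factor that allocation is balanced on; a stratified test is a small, nearly free efficiency gain, not the correction of an error

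*Combined protocol and SAP*

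**What the plan says.** Section 4, under recruitment procedures, gives both the balancing factor and the reason for it: "Based on prior work demonstrating differences in STI and pregnancy testing due to presence of genito-urinary symptoms, we will ensure balanced allocation". The ratio is 1:1. Assignment is by a computer-generated algorithm and sealed envelopes; neither strata nor blocks are named.

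Section 7 defines the primary outcome as "the proportion of participants in each arm who receive any health service". The list of services includes STI and pregnancy testing. The arms are then compared "using tests of the differences between two sample proportions", with no stratum or covariate. Section 7 mentions multivariate methods for condom use, not for this outcome.

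GU status is available before randomisation. Section 8 describes the first consent phase as "screening for eligibility and GU complaints with the health survey".

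**The concern.** The trial treats GU complaint as important enough to control in the design and then drops it from the analysis. When a factor is prognostic and allocation is balanced on it, the difference between arms varies less from trial to trial than an unstratified standard error assumes. The crude test then becomes conservative and the crude interval wider than it needs to be.

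This does not threaten validity: the crude difference is unbiased and, under exact balance, stratifying leaves the estimate unchanged. What is at stake is some power, and some precision in the effect size that Sections 7 and 9 say will support a later multi-site application.

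**Working it through.** **Inputs from Section 7.** Two-sided alpha .05; design rates .15 (control) and .50 (intervention); expected rates .08 and .65; 38 per arm in the power calculation and 40 per arm recruited; stated power .94, or .84/.91 (two-/one-tailed) with 25% attrition.

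**Assumed, because the documents do not say.** GU share 30% (varied from 10% to 50%); GU odds ratio (OR) for the outcome 1, 2, 4 or 8, either in both arms or in controls only.

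**The plan's own figures.** At 38 per arm the unpooled standard error is √[(.15×.85 + .50×.50)/38] = √(.3775/38) = .0997. Power is Φ(.35/.0997 − 1.96) = Φ(1.55) = .94, as stated. The pooled form at 30 per arm gives .843 and .911, matching .84/.91.

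**Where the gain comes from.** Take OR 8 in both arms, 30% GU. The rates (GU/non-GU) that average to .15 and .50 are .352/.064 and .820/.363.

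- Control within-stratum variance: .3×.352×.648 + .7×.064×.936 = .110, against .1275 crude.
- Intervention: .3×.820×.180 + .7×.363×.637 = .206, against .250 crude.
- Standard error at 40 per arm: √(.316/40) = .089, against √(.3775/40) = .097.

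At OR 2 (rates .217/.121 and .620/.449) the two sums are .369 and .3775, so the standard errors differ by about 1%.

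**Tests compared.** The crude test is the pooled z-test. For CMH without continuity correction, a stratum with k per arm, x intervention successes and m successes in total contributes x − m/2 to the numerator and m(2k − m)/[4(2k − 1)] to the variance; z is the summed numerator over the square root of the summed variance. Power comes from exact enumeration of the four binomials (arm by GU stratum), with 12 GU of 40 or 11 GU of 38 per arm.

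| Scenario | Quantity | OR 1 | OR 2 | OR 4 | OR 8 |
|---|---|---|---|---|---|
| .15 vs .50, 40/arm, both arms | crude power | .933 | .935 | .940 | .948 |
| | CMH power | .934 | .938 | .951 | .969 |
| | gain (points) | 0.1 | 0.3 | 1.1 | 2.0 |
| .15 vs .50, 40/arm, controls only | gain | 0.1 | 0.1 | 0.2 | 0.5 |
| .15 vs .50, 38/arm, both arms | gain | −0.4 | 0.0 | 1.0 | 1.9 |
| .15 vs .50, 38/arm, controls only | gain | −0.4 | −0.3 | −0.1 | 0.2 |
| .15 vs .36, 40/arm, both arms | gain | 0.2 | 0.7 | 3.1 | 7.5 |
| .08 vs .29, 40/arm, both arms | gain | −0.1 | 0.2 | 1.7 | 4.8 |

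The last two rows use a difference of .21 because Section 7 says "we will have power to detect differences as small as .21" without giving a control rate. With GU prognostic in controls only, those gains fall to at most 1.0 and 0.1 points. At the expected .08 vs .65, both tests have power of essentially 1. Over GU shares of 10% to 50%, the OR 8 gain at 40 per arm is 1.3 to 2.0 points (.15 vs .50) and 4.3 to 7.5 points (.15 vs .36).

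**Type I error, 40 per arm, OR 1/2/4/8.**

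- Common rate .325: crude .048/.045/.037/.026; CMH .049/.048/.049/.050.
- Common rate .15: crude .053/.052/.046/.038; CMH .051/.051/.050/.050.

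**95% interval at .15 vs .50, 40 per arm, OR 1/2/4/8.**

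- Coverage: crude Wald .943/.946/.953/.962; Mantel-Haenszel with Sato variance .942/.942/.942/.944; Mantel-Haenszel with plug-in stratum variances .938/.937/.937/.937.
- Mean width: crude .376 throughout; Sato .375/.372/.362/.347.

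**If balance is left to chance** (simulation, 400,000 trials per scenario, 40 per arm). At a common rate of .325 the crude type I error is about .048, and crude coverage at .15 vs .50 is about .943, at every OR. The CMH gain at .15 vs .50 is then −0.1/0.3/1.6/3.3 points (both arms) or −0.2/0.0/0.3/0.9 (controls only).

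**The case against.** The strongest reply is that nothing here is broken. The crude test is valid, the trial has about .93 power at its design rates with 40 per arm, and at the expected rates neither test can miss. A gain above about half a point at .15 vs .50 needs an OR of around 4 or more in both arms if balance is enforced, and the documents offer no such figure. All of that stands.

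There are also reasons in the documents to expect a weak effect. The composite counts condoms, contraception, HIV testing and referral as well as STI and pregnancy tests. Section 3 leaves out "services that are completed via a standing order or protocol". GU complaint may act mainly among controls, of whom Section 3 says "Participants will then be referred back to their ED provider, who will provide their standard care". Intervention services are instead offered "Based on behaviors, CDS system recommendations (generated from screening survey responses only for intervention participants), and discussions".

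The 7.5-point figure belongs to a setting (.15 vs .36) where the trial is underpowered with either test: .596 crude and .670 CMH. It should not be read as the expected benefit.

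Nor does the Sato interval improve coverage. At .15 vs .50 it runs slightly under 95%. At .08 vs .65 it gives .934/.936/.940/.943, against .934/.936/.942/.949 for the crude interval. Its merit is a shorter interval when GU is strongly prognostic, at a coverage shortfall of under one point at the design rates.

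Finally, Section 4 does not say how balance is enforced. If it is left to chance, the argument that the crude test is conservative disappears. The stratified test still gains slightly in that case, so the recommendation does not depend on the mechanism.

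**Conclusion.** The point holds as a minor improvement that the sponsor should consider. Allocation is balanced on GU complaint, the primary test ignores it, and none of the plan's stated figures becomes wrong as a result.

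At the design rates, stratifying is worth about 0 to 2 points of power under enforced balance. It is worth close to nothing if the OR is 2 or less or if GU matters mainly in controls, and it costs at most about 0.4 points at 38 per arm if GU does not matter. The crude interval is materially too wide only at about OR 8 (.376 against .347).

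These sizes rest on an assumed GU share and OR. That the analysis does not use the balancing factor does not depend on any assumption.

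**What to change.** In Section 7, pre-specify as the primary analysis a CMH test stratified by the GU-complaint factor used for allocation, as recorded on the screening survey. Report the Mantel-Haenszel risk difference with a 95% confidence interval using the Sato variance rather than plug-in stratum variances; this keeps the planned difference-in-proportions scale. Retain the crude two-proportion test as a supportive analysis.

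The cost is one or two sentences. GU complaint is already collected before randomisation, the calculations are closed-form on two 2×2 tables, and no extra data or participants are needed. Writing it down before the data are seen avoids any suggestion that the adjustment was chosen for its result.
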